## 12.0 Participant Information

### 12.1 Subject Population:

The subject population consists of 158 active duty and returning Operation Iraqi Freedom (OIF), Operation Enduring Freedom (OEF), and Operation New Dawn (OND) veterans, aged 18 to 65 with a

diagnosis of PTSD despite adequate trial of medication treatment (8 weeks) (e.g., CAPS score greater than or = 40).

Subjects will be recruited from collaborator- and provider-referrals at WRNMMC and the Syracuse VA Medical Center, as well as from associated community-based outpatient clinics (CBOCs) and other referring research studies.

### 12.2 Age Range:

- 0-17
- 18-24
- 25-34
- 35-44
- 45-54
- 55-64
- 65-74
- 75+

### 12.3 Gender:

- Male
- Female

### 12.4 Special categories:

- Minors /Children - "You must also consider the requirements of 45 CFR 46 Subpart D and DoDI 3216.02, Enclosure 3, paragraph 7.d."
- Students
- Employees - Civilian - "You must also consider the requirements of DoDI 3216.02, paragraph 7.e."
- Employees - Contractor
- Resident/trainee
- Cadets /Midshipmen - "You must also consider the requirements of DoDI 3216.02, Enclosure 3, paragraphs 7.e. and 12."
- Active Duty Military Personnel - "You must also consider the requirements of DoDI 3216.02, Enclosure 3, paragraph 7.e."
- Wounded Warriors - "Depending on your intended subjects' status, you may also need to consider the requirements of DoDI 3216.02, Enclosure 3, paragraph 7.e."
- Economically Disadvantaged Persons - "You must also consider the requirements of 32 CFR 219.111 (b)."
- Educationally Disadvantaged Persons - "You must also consider the requirements of 32 CFR 219.111 (b)."
- Physically Challenged (Physical challenges include visual and/or auditory impairment)
- Persons with Impaired Decisional Capacity - "You must also consider the requirements of 10 USC 980."
- Prisoners - "You must also consider the requirements of 45 CFR 46 Subpart C and DoDI 3216.02, Enclosure 3, paragraphs 7.b. and 7.c."
- Pregnant Women, Fetuses, and Neonates
- Non-English Speakers
- International Research involving Foreign Nationals - Headquarters Review is necessary

### 12.5 Inclusion Criteria:

Order Number	Criteria

a. **Inclusion Criteria** – Male and female subjects, aged 18 to 65 are eligible for inclusion in the study if they satisfy the following criteria:

1

1. Are an active-duty service member or an Operation Iraqi Freedom (OIF), Operation Enduring Freedom (OEF), or Operation New Dawn (OND) veteran.
2. Are diagnosed with PTSD and have not achieved remission with an adequate trial of medication treatment (8 weeks) as indicated by self-report at referral and confirmed by baseline CAPS score of greater than or = to 40 after informed consent is obtained.

## 12.6 Exclusion Criteria:

Order Number	Criteria
	
b. Exclusion Criteria - Subjects will be excluded from the study for any of the following reasons:
 
 
1. Female subjects of childbearing capacity who test positively for <math>\beta</math>-HCG, or are either self-reporting as pregnant, planning to become pregnant, or nursing.
 
2. Presence of psychotic features.
 
3. Unable to provide informed consent or comply with study procedures.
 
4. Previous treatment with riluzole.
 
5. Serious, unstable illnesses including hepatic, renal, gastroenterological, respiratory, cardiovascular (including ischemic heart disease), endocrinologic, neurologic, immunologic, hematologic disease, or HIV. This includes individuals with a history of COPD by diagnosis as well as persons taking inhalers for Asthma or Reactive Airway Disease.
 
6. Clinically significant abnormal levels (3x ULN or greater) of serum transaminases (ALT/SGPT; AST/SGOT), current or past blood dyscrasia.
 
7. Subjects with uncorrected hypothyroidism or hyperthyroidism.
 
8. DSM-IV alcohol or substance abuse or dependence within 90 days of the screening visit.
 
9. Treatment with a reversible MAOI, guanethidine, or guanadrel within 1 week, or any change in fluoxetine dosing within 8 weeks prior to visit 2. Use of antidepressant and sedative/hypnotic drugs at stable dose is permitted.
 
10. Documented history of hypersensitivity or intolerance to riluzole.
 
11. Subjects with a current or past history of other axis I disorders including schizophrenia, schizoaffective disorder, bipolar disorder or dementia. However, those with a co-morbid history of other Axis I disorder like major depression, dysthymia or other anxiety disorders will be included; the justification for this is that approximately 70% of subjects with PTSD have co-morbid depression and or alcohol abuse, and restricting the sample to PTSD patients without depression will not accurately reflect the scope of this disorder.
 
12. Patients who are currently at high risk for homicide or suicide, as indicated by an affirmative answer to the question: "In the last three months, have you attempted to kill yourself, made specific plans to kill yourself, or had the intention to kill yourself?"
 
13. Current or planned litigation regarding the traumatic event.
 
14. Patients who recently started trauma focused cognitive behavioral psychotherapy (Patient's underlying educational or supportive individual or group therapy will be included).
 
15. Patient's actively enrolled in an evidence based psychotherapy treatment (e.g., Cognitive Processing Therapy or Prolonged Exposure Therapy) will be excluded until that therapy has concluded, but may be re-approached at that time if patient self-report or clinician referral suggests persistent PTSD symptoms upon conclusion of that treatment.
 
16. Subjects with an artificial cardiac pacemaker or metallic implants within their body will be enrolled at WRNMMC for the placebo-control clinical trial portion of the study only. These individuals, due to their pre-existing medical condition, are medically ineligible to participate in the <math>^1\text{H}</math> MRS imaging portion of the study. Further, the Magnetic Resonance (MRI) Screening Form is use at WRNMMC will be used for participant screening prior to any imaging procedures.
 
17. Use of benzodiazepines.
 

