
**Rationale and further discussion for General Inclusion and Exclusion criteria**

Age criteria: The absence of data demonstrating the efficacy and tolerability of riluzole in children with PTSD makes their inclusion unethical.

Diagnosis: Subjects with other co-morbid Axis I disorders except for major depressive disorder and other anxiety disorders are excluded because patients with this characteristic may constitute a group with a more severe form of illness that requires a different treatment approach. Patients with a co-morbid diagnosis of major depressive disorder will be included because of the frequent co-occurrence of major depression in patients with PTSD.

Severity criteria: Only subjects with a certain severity of PTSD will be included to increase the likelihood of finding the desired results. That is, PTSD must be unremitting and under current treatment on a stable prescriptive dosage for a minimum of 8 weeks on either of the two FDA-approved drugs for PTSD (Paroxetine – Paxil or Sertraline – Zoloft) or any other SSRI/SNRI in off-label prescriptive use for the management of PTSD. A score of 40 or more on CAPs is also required.

Exclusion of recent substance abuse or dependence: We elect to use a narrower exclusion criterion of abuse and dependence than DSM-IV (within the past three months) in order to allow participation by subjects with a history of substance abuse or dependence problems that could be secondary to their mood disorders. Allowing participation by patients with histories of substance abuse/dependence more than three months earlier broadens the inclusion criteria to more closely approximate patients seen in “real world” settings. Study medications are not associated with increased risk of future dependence problems.

To safeguard participants from self-incrimination, two exclusion criteria will be grouped and presented using the following script, which will be read aloud to each potential participant as part of obtaining informed consent for study enrollment:

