“There are two situations that would preclude you from participating in this study. I’m going to read these two to you. If you believe that either of these is relevant to you, you cannot be in this study. You do not need to state what your personal reasons are to me. And I will not record them in any manner. If you can participate in this study, please state, ‘**YES**’ when I ask you if you’d like to be in the study. You do not need to say, ‘**NO**’ if you cannot be in the study. Simply say ‘**THANK YOU**’, and I will understand. I appreciate your time and consideration in participating.

The two situations are:

1. In the past 90 days, have you struggled with significant alcohol or substance abuse?
2. Are you planning to file legal suit or seek litigation regarding your traumatic event?

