All subjects will be evaluated for study entry during the Screening Visit by a Masters-level Clinical Research Psychologist under the supervision of a credentialed provider within the WRNMMV Behavioral Health Clinic using a CAPS assessment; WRNMMC study research staff will recruit, screen, consent and enroll subjects at WRNMMC, while Syracuse VA Medical Center study research staff will recruit, screen, consent and enroll subjects at the Syracuse VA Medical Center, as well as from associated community-based outpatient clinics (CBOCs). CAPS score  $\geq$  40 will be necessary for study enrollment. Those entering the study at the completion of an INTRuST medication trial will also receive a CGI assessment, and must have an assessment determination of "NOT improved" or "NOT very much improved" on the CGI at the completion of their medication trial to be eligible for study enrollment.

The Screening Visit will include all screening tests, patient and family history, and psychiatric and physical examinations, as well as menstrual history in females. Inclusion and exclusion criteria will be assessed. Subjects will undergo a physical exam, supine and standing vital signs, blood chemistries, liver function tests, hematology profile, urinalysis (including screens for substances of abuse), hepatitis screen, SCID, and CAPS. Women of childbearing capacity will have baseline serum  $\beta$ -HCG, and a positive  $\beta$ -HCG will exclude them from participating in the study. Subjects must also have a negative Human Immunodeficiency Virus (HIV) test.

A complete medication list will be compiled prior to dispensing riluzole and verification of the list for change will be done at the weekly clinical visit to assess for compounds that may interact with clearance of the drug.

Participants will be advised to take riluzole 1 hour before or two hours after meals for optimal metabolism of the compound. Education will be provided that the bioavailability of the compound is significantly affected by high fat meals and that charbroiled food may increase the speed of clearance of the compound from their bodies.

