Further, if during the weekly visit, a participant's response to the research battery indicate increasingly severe physiological or psychological symptoms that require an immediate intervention or they express suicidal ideation, intent, or plan, study staff will promptly notify the Principal Investigator for referral and treatment management of the individual. As part of study enrollment, participants will be given the 24-hour emergency contact information for the Investigators and will receive careful instruction on how to reach members of the research team for assistance. Finally, before enrolling in the study, participants will be asked to complete a Treatment Contract. In the Treatment Contract participants will identify a doctor, family member or friend who is aware of their participation in this research study and is willing to be a part of their support system. The Investigator may contact the person(s) who have agreed to act as the participant's support system in the case their symptoms worsen during the study or there is an emergent medical issue that requires immediate contact.

*End of treatment/early discontinuation for the trial:*

Participants may withdraw at any time or be removed from the study at the discretion of the Investigator, should medical contraindications to the assigned medication develop, if intolerable adverse reactions occur, if mood or anxiety worsens, or if in the clinician's judgment the patient has worsened to such a degree that further participation would put the individual at risk. If a participant begins evidence based psychotherapy (such as CPT or prolonged exposure therapy) or if any of the medications the participant takes for PTSD or other psychiatric conditions are changed after they begin the study, the participant may be withdrawn from the study. Participants are at no risk of losing their right to medical care and some period of observation by the investigators may be recommended for the participants to safely stop taking part in the study because of the study drug.

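### Exclusion item 12 names homicide or suicide risk but decides it by a question about suicide only; a lesser mismatch is that the consent script for item 13 omits litigation already under way

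*Combined protocol and SAP*

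**What the plan says.** Section 12.6, item 12, excludes "Patients who are currently at high risk for homicide or suicide, as indicated by an affirmative answer to the question". The question is then given in full: "In the last three months, have you attempted to kill yourself, made specific plans to kill yourself, or had the intention to kill yourself". Item 13 of the same list excludes "Current or planned litigation regarding the traumatic event".

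The rationale text after the exclusion list says that, to protect candidates from self-incrimination, "two exclusion criteria will be grouped and presented using the following script". The script is read aloud to each candidate as part of consent. Its first situation concerns recent alcohol or substance abuse. Its second asks: "Are you planning to file legal suit or seek litigation regarding your traumatic event". Candidates are told to decline if they believe either situation is relevant to them, and also: "You do not need to state what your personal reasons are to me. And I will not record them in any manner".

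Section 13.2 says of the Screening Visit that "Inclusion and exclusion criteria will be assessed". That visit includes a psychiatric examination and the SCID. The Safety Monitoring Plan in Section 14.2 has study staff notify the principal investigator if weekly responses show worsening symptoms needing immediate intervention, or if "they express suicidal ideation, intent, or plan". Sections 13.1 and 13.4, on subject selection and eligibility assessment, refer to a legacy protocol that was not supplied.

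**The concern.** An exclusion rule has two parts: what it means to keep out, and how a candidate is found to belong to that group. In item 12 the parts disagree within one sentence. The rule names two risks, and the phrase introducing the question makes the answer the indicator for both, yet the question addresses one.

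Item 12 is a safety exclusion in a placebo-controlled trial of service members and veterans whose PTSD has not remitted on medication. Staff at either site who follow the text exactly would class a candidate with homicidal intent alone as not meeting it. Staff who follow the evident purpose would do otherwise. The rule is therefore not reproducible between raters or between WRNMMC and the Syracuse VA.

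Item 13 matters less. The sponsor chose to keep litigants out of a trial whose outcomes are interview and self-report scales, and the wording put to candidates is narrower than that choice.

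**Working it through.** No arithmetic applies. The check compares each criterion with the question that puts it into effect, then looks for another passage that fills any gap.

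**Item 12: coverage.** The criterion names two risks, homicide and suicide. The question has three limbs (an attempt, specific plans, an intention), each directed at oneself. Coverage is one risk of two.

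**Item 12: literal application.**

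| Candidate in the last three months | Truthful answer | Result under the stated test | Named in the criterion? |
|---|---|---|---|
| Suicidal plan only | Yes | Excluded | Yes |
| Suicidal and homicidal plans | Yes | Excluded | Yes |
| Homicidal plan only | No | Not excluded | Yes |
| Neither | No | Not excluded | No |

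Only the third row goes wrong, and it does so whenever the test is applied as written.

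**Item 12: is the gap filled elsewhere?** Homicide is mentioned nowhere else in the supplied text.
- The general eligibility check in Section 13.2 leads back to item 12 and its question.
- The psychiatric examination and the SCID have no stated homicide item and are not linked to item 12.
- The Section 14.2 triggers apply after enrolment. They cover severe psychological symptoms in general, and suicidality by name.

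**Item 13: coverage.** The criterion names two states, current and planned, and is complete in itself. The gap lies in the script, which uses forward-looking wording.

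| Candidate | Meets item 13? | Does the script's wording apply? |
|---|---|---|
| Suit planned | Yes | Yes |
| Suit filed, nothing further planned | Yes | Unclear: no longer planning to file, but may read the wording on seeking litigation as applying |
| Neither | No | No |

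**Item 13: is the gap filled elsewhere?** The script's other situation, substance abuse, has further checks at screening in the SCID and the urine drug screen. The supplied text describes no second check for litigation beyond the general statement in Section 13.2. Because reasons are not recorded, the script leaves nothing from which a current litigant could be identified later.

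**The case against.** The strongest case on the other side is that practice would be safer than the wording. Screening includes a psychiatric examination and a structured interview, and the protocol says screening results serve to find conditions that would make randomization less safe. The investigator may remove a participant whose condition worsens. The eligibility procedure itself sits in a legacy protocol that cannot be seen here. Much of this stands: it makes entry of such a patient less likely, and the point claims only that entry is possible. It does not remove the contradiction, because the deciding question is written out in full in this document. A fuller legacy rule would conflict with it and would also need reconciling.

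On litigation the objection is stronger. The script is described as a way of presenting the criterion, not as the only test of it. The instruction to decline if a situation seems relevant is broad, and the criteria are to be assessed at screening. Not recording reasons is a deliberate privacy protection and is not criticised here. What remains is a word missing from the script.

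A reader might infer more than the text supports, in five ways:
- **That item 13 is itself defective.** It is not; only the script is narrower.
- **That the script misses every current litigant, or forbids them to speak.** Some would recognise themselves in it, and it says only that reasons need not be given.
- **That on-study monitoring covers suicidality alone.** The same sentence also covers severe psychological symptoms generally.
- **That half of the patients concerned are missed.** One of two is a count of named categories, not of people.
- **That power suffers.** The documents give neither the share of litigants nor their response to treatment, so any such figure would be invented. The sample size calculation in Section 11.2 is unaffected.

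**Conclusion.** The point stands for item 12. The stated test cannot indicate one of the two risks the criterion names, and no other supplied passage specifies a screen for it. For item 13 there is a lesser inconsistency between a complete criterion and a narrower script.

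The size is categorical: one of two named risks is untested in item 12, and one of two named states is not expressly asked about in the item 13 script. How many candidates this affects cannot be estimated from the documents. The conclusion assumes that the question in item 12 is applied as written and that no unsupplied text overrides it. It does not assume that any such patient has been or will be enrolled.

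**What to change.** Reconcile the two halves of item 12. Either the deciding test covers every risk the criterion names, or the criterion names only what the test covers. The sponsor and the investigator should choose between these and set any clinical screening content.

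In the consent script, add current litigation to the second situation so that it matches item 13. The privacy arrangement can stay as it is. If the legacy protocol contains fuller wording on either rule, bring the two documents into agreement in the same amendment.

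The cost is a short change to the protocol and script, and possibly a few more screen failures. The rewording itself requires no new visit or procedure.

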
**Rationale and further discussion for General Inclusion and Exclusion criteria**

Age criteria: The absence of data demonstrating the efficacy and tolerability of riluzole in children with PTSD makes their inclusion unethical.

Diagnosis: Subjects with other co-morbid Axis I disorders except for major depressive disorder and other anxiety disorders are excluded because patients with this characteristic may constitute a group with a more severe form of illness that requires a different treatment approach. Patients with a co-morbid diagnosis of major depressive disorder will be included because of the frequent co-occurrence of major depression in patients with PTSD.

Severity criteria: Only subjects with a certain severity of PTSD will be included to increase the likelihood of finding the desired results. That is, PTSD must be unremitting and under current treatment on a stable prescriptive dosage for a minimum of 8 weeks on either of the two FDA-approved drugs for PTSD (Paroxetine – Paxil or Sertraline – Zoloft) or any other SSRI/SNRI in off-label prescriptive use for the management of PTSD. A score of 40 or more on CAPs is also required.

Exclusion of recent substance abuse or dependence: We elect to use a narrower exclusion criterion of abuse and dependence than DSM-IV (within the past three months) in order to allow participation by subjects with a history of substance abuse or dependence problems that could be secondary to their mood disorders. Allowing participation by patients with histories of substance abuse/dependence more than three months earlier broadens the inclusion criteria to more closely approximate patients seen in “real world” settings. Study medications are not associated with increased risk of future dependence problems.

To safeguard participants from self-incrimination, two exclusion criteria will be grouped and presented using the following script, which will be read aloud to each potential participant as part of obtaining informed consent for study enrollment:

“There are two situations that would preclude you from participating in this study. I’m going to read these two to you. If you believe that either of these is relevant to you, you cannot be in this study. You do not need to state what your personal reasons are to me. And I will not record them in any manner. If you can participate in this study, please state, ‘**YES**’ when I ask you if you’d like to be in the study. You do not need to say, ‘**NO**’ if you cannot be in the study. Simply say ‘**THANK YOU**’, and I will understand. I appreciate your time and consideration in participating.

The two situations are:

1. In the past 90 days, have you struggled with significant alcohol or substance abuse?
2. Are you planning to file legal suit or seek litigation regarding your traumatic event?

